8.6 Expectedness of SAEs

The nature or severity of the event must be considered with reference to the applicable product information, for example the most recent Summary of Product Characteristics (SPC) or Investigator Brochure. If the nature or severity of the event is inconsistent with the SPC or IB the event must be classified as unexpected.

8.7 Expected SAEs for specific drugs/treatments

All investigators should refer to the Investigator Brochure for Panitumumab when determining whether a SAE is expected. The CTRU will ensure that any updates are circulated to all investigators. Any SAE's not listed in Appendix A of the Investigator Brochure should be classed as 'unexpected'.

The following table lists side effects/potential SAEs listed in the SPC for the irinotecan and ciclosporin and should therefore usually be considered as expected events and thus would not meet the criteria of SUSAR. The table should be used as a guide only and the most recent and relevant SPC must be referred to for more specific details and potential drug interactions.

Toxicity	Irinotecan	Ciclosporin
Biochemistry		
Alkaline phosphatase increase (mild to moderate)	✓	
Amylase increase (rare)	✓	
Bilirubin increase (mild to moderate)	✓	
Creatinine increase (mild to moderate)	✓	
Lipase increase (rare)	✓	
SGPT (grades 1-2)	✓	
SGOT (grades 1-2)	✓	
Transaminase increase (mild to moderate)	✓	

Toxicity	Irinotecan	Ciclosporin
Cardiovascular		
Cardio-circulatory failure (infrequent)	✓	
Hypertension	✓ (rare)	✓
Hypotension (infrequent)	✓	
Cutaneous		
Allergic rash		✓
Alopecia	✓	
Hypertrichosis		✓
Mild cutaneous reaction	✓	
Gastrointestinal		
Abdominal pain	✓	✓
Anorexia	✓	✓
Colitis (ischemic and ulcerative)	✓	
Delayed diarrhoea	✓	
Diarrhoea	✓	✓
Gastrointestinal haemorrhage	✓	
Gingival hyperplasia		✓
Intestinal obstruction	✓	
Intestinal perforation	✓	
Ileus	✓	
Mucositis	✓	
Nausea	✓	✓
Typhlitis	✓	
Vomiting	✓	✓
Haematological		
Anaemia	✓	✓
Febrile neutropenia	✓	
Haemolytic uraemic syndrome		✓
Hyperglycaemia		✓
Hyperkalaemia		✓
Hyperlipidaemia		✓
Hyperuricaemia		✓
Hypokalemia (rare)	✓	
Hypomagnesaemia		✓
Hyponatremia (rare)	✓	
Micro-angiopathic haemolytic anaemia		✓
Neutropenia	✓	
Sepsis	✓	
Thrombocytopenia	✓	✓
Neurotoxicity		
Encephalopathy/ demyelination (signs including convulsions, confusion, disorientation, decreased responsiveness, agitation, insomnia, visual disturbances, cortical blindness, coma, paresis, cerebellar ataxia)		✓
Headache		✓
Motor polyneuropathy		✓

Toxicity	Irinotecan	Ciclosporin
Neurotoxicity continued...		
Optic disc oedema (incl. papilloedema with possible visual impairment secondary to Benign Intracranial Hypertension) (very rare)		✓
Paresthesia	✓	✓
Tremor		✓
Dyspnoea	✓	
Interstitial pulmonary disease (uncommon)	✓	
General		
Acute cholinergic syndrome (early diarrhoea, abdominal pain, conjunctivitis, rhinitis, hypotension, vasodilatation, sweating, chills, malaise, dizziness, visual disturbances, myosis, lachrimation, increased salivation)	✓	
Allergic reaction	✓	
Anaphylactic/ anaphylactoid reaction	✓	
Asthenia	✓	
Dehydration	✓	
Fatigue		✓
Fever	✓	
Gynaecomastia		✓
Hepatic dysfunction		✓
Infection	✓	
Infusion reaction (fever, chills, rigors, shakes, hypotension)	✓	
Menstrual disturbances		✓
Muscular contraction/ cramps	✓	✓
Muscle weakness		✓
Myalgia		✓
Myopathy		✓
Oedema		✓
Pancreatitis		✓
Renal dysfunction		✓
Renal insufficiency (infrequent)	✓	
Transient speech disorders (very rare)	✓	
Weight increase		✓

8.7 Pharmacovigilance responsibilities

Local investigator:

1. Medical judgement in assigning to AEs:
 - Seriousness
 - Causality
 - Expectedness
2. To fax SAE form to CTRU within 24 hours of becoming aware and to provide further follow-up information as soon as available
3. To report SAEs to local committees in line with local arrangements

Chief Investigator (or nominated individual in CI's absence):

1. Chief Investigator to assign causality and expected nature of SAEs where it has not been possible to obtain local assessment
2. Chief Investigator will review all events assessed as SAEs in the opinion of the local investigator
3. Chief Investigator to review all events assessed as SUSARs in the opinion of the local investigator. In the event of disagreement between local assessment and Chief Investigator review with regards to SUSAR status, local assessment will not be overruled, but Chief Investigator may add comments prior to reporting to MHRA.

CTRU:

1. Report SAEs relating to patients on the IrPan arm to Amgen within 1 working day
2. Expedited reporting of SUSARs to MHRA and main REC within required timelines
3. Preparing annual safety reports to MHRA and main REC
4. Preparing safety reports for the DMEC at 3-monthly intervals for SAEs
5. Notifying Investigators of SUSARs which compromise patient safety
6. Distributing CIOMs line listings, as provided by Amgen quarterly, to Investigators and main REC on a regular basis

TSC:

1. Role in reviewing safety data and liaising with the DMEC regarding safety issues, as required

DMEC:

1. 3-monthly review of unblinded overall safety data to determine patterns and trends of events, or to identify safety issues, which would not be apparent on an individual case basis
2. Review of interim analysis

AMGEN INC:

1. Reporting all SUSARs related to panitumumab to the Global Regulatory Authorities, except to MHRA, within the required timelines
2. Providing the CTRU with quarterly Investigator CIOMs line listings
3. Review all SAEs relating to patients on the IrPan arm and inform CTRU of any upgrades to SUSAR

9. CRITERIA OF RESPONSE

Response to treatment will be assessed using the Response Evaluation Criteria in Solid Tumours (RECIST), please refer to Appendix 1. Responses will be confirmed by central review. External confirmation of RECIST response data will be performed on all baseline and 12-week scans.

The baseline and subsequent CT scans (film copies or CD data copies) will be forwarded to the CTRU for external radiological review (see section 5.3).

10. ENDPOINTS

10.1 Primary Endpoint

Ir vs IrCs comparison

- Proportion of patients progression-free 12 weeks after randomisation.

Ir vs IrPan comparison (patients with wild-type K-RAS status not previously receiving an anti-EGFR targeted therapy)

- Overall survival (OS) from randomisation

10.2 Secondary Endpoints

Ir vs IrCs comparison

- Proportion of patients free from treatment failure at 12 weeks
- Overall survival (OS) from randomisation
- Research nurse-assessed toxicity (NCI-CTC[V3] grades): maximum toxicity grade per patient; rate per cycle; all-cause mortality within 60 days of randomisation; toxicity of primary interest is grade 3+ diarrhoea within 12 weeks of randomisation;

Ir vs IrPan comparison (patients with wild-type K-RAS status not previously receiving an anti-EGFR targeted therapy)

- Proportion of patients progression-free 12 weeks from randomisation.
- Research nurse-assessed toxicity (NCI-CTC[V3] grades): maximum toxicity grade per patient; rate per cycle; all-cause mortality within 60 days of randomisation;

Ir vs IrCs and Ir vs IrPan (patients with wild-type K-RAS status not previously receiving an anti-EGFR targeted therapy) comparisons

- Progression-free survival (PFS) from randomisation
- Best response by RECIST criteria within 1-year follow-up from randomisation
- Patient-assessed symptom/QL/PA scores at 12 and 24 weeks

10.3 Exploratory Endpoints

Ir vs IrPan comparison (patients with wild-type K-RAS status previously receiving an anti-EGFR targeted therapy)

- Proportion of patients progression free 12 weeks after randomisation.
- Research nurse-assessed toxicity (NCI-CTC[V3] grades): maximum toxicity grade per patient; rate per cycle; all-cause mortality within 60 days of randomisation;

Ir vs IrPan comparison (patients randomised to receive Ir or IrPan under Protocol Version 1.0 who have mutant or unknown K-RAS status, regardless of previous anti-EGFR targeted therapy)

- Proportion of patients progression free 12 weeks after randomisation.
- Research nurse-assessed toxicity (NCI-CTC[V3] grades): maximum toxicity grade per patient; rate per cycle; all-cause mortality within 60 days of randomisation;

10.4 Choice of Primary Endpoint

Ir vs IrCs comparison

A non-inferiority trial requires a sensitive discriminator of efficacy. To use PFS for this purpose would require CT scanning at a frequency close to the difference being excluded, which in this trial is less than 6 weeks. Response rate is insensitive given the low rate of objective responses (<10%) with the standard therapy. OS is subject to influence by subsequent treatment. In contrast the proportion of patients free of progression at 12 weeks can be determined reliably with a single mandatory scan/assessment point, and the expected progression-free proportion of approximately 65% with standard therapy is a good basis for comparison.

Ir vs IrPan comparison (patients with wild-type K-RAS status not previously receiving an anti-EGFR targeted therapy)

The choice of OS for the primary endpoint for the +/- panitumumab comparison reflects the fact that for a novel therapy to be adopted into standard care, given known skin toxicity and likely cost, it would require a significant tangible benefit, and OS is objective and well accepted. Worthwhile treatment given at a relatively late stage in the disease should produce an OS effect. Furthermore this endpoint is reliable and avoids the need for very frequent scanning which is both arduous for patients and expensive. Hence our primary endpoint for the +/- panitumumab comparison is OS. The use of three secondary efficacy endpoints (PFS; RR; Progression-free at 12 weeks) ensures that a lesser efficacy benefit, requiring further phase III trials, would not go un-noticed.

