5.3 Baseline and reassessment CT scan

The baseline CT scan **must be within 4 weeks prior to the start of trial treatment**, so a repeat CT should be organised if required, remembering that randomisation cannot take place until *K-RAS* mutation status has been determined. Limited funding is available to contribute towards the cost of repeat baseline CT scans that are required only to meet the timelines set out in this protocol. Funding is available up to a limit of £150 per-patient at the time of writing this protocol. Please contact the CTRU for current funding availability.

Radiological reassessment is made **12 weeks after randomisation** ("12 week scan"), then at 12-weekly intervals, or sooner if clinically indicated, until disease progression ("follow-up scans"). It is recommended that the 12 week scan is pre-booked, at the time of starting treatment, **as near as possible to exactly 12 weeks after the date of randomisation** (with up to a further two weeks allowed in order to take account of practical issues).

If there is clinical evidence of disease progression at a time other than when radiological reassessment is due a CT scan should be carried out to confirm progression. A CT scan should always be carried out to confirm disease progression, unless there is a compelling reason not to.

Please note that copies of the baseline and the 12 week scan are required for external review. The preferred format is CD Rom, but hard-copy films are also acceptable. These should be forwarded to the PICCOLO team, CTRU, University of Leeds, [name] with their reports, as soon as possible after the 12 week scan has been performed. The scans and reports should be anonymised and labelled with the patient's trial number only. CTRU will provide pre-paid Special Delivery envelopes in which to send the CT scans for central review.

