11. STATISTICAL CONSIDERATIONS

11.1 Sample Size

Ir vs IrCs comparison

A non-inferiority design is proposed, based upon the proportion of patients progression-free at 12 weeks from randomisation. In a previous study in a similar patient population receiving irinotecan, median PFS was 4.2 months, with 63.3% of patients progression-free at 12 weeks.³⁸ There are no previous best supportive care (BSC) trials that have included regular CT scan assessments, however in a trial comparing irinotecan with BSC, at the time point that 63% of Ir

patients were alive, less than 40% of BSC patients were alive⁴⁰. On this basis we have estimated that a similar proportion – 40% - of patients on BSC would be expected to be progression-free at 12 weeks applying standard WHO or RECIST criteria. On this basis irinotecan contributes at least 23% to the proportion of patients progression-free at 12 weeks. On the basis of clinician consensus IrCs will be defined as no worse than Ir if median PFS is at least 3 months with IrCs, equivalent to at least 52.7% of patients in the IrCs arm progression-free at 12 weeks. This corresponds to a reduction of no more than 10.6% in the proportion of patients progression-free at 12 weeks which is our non-inferiority margin; retaining more than half the effect that irinotecan has over BSC. The sample size calculation for the Ir vs. IrCs comparison remains the same since there is no data to suggest that *K-RAS* status is a predictive factor for Irinotecan or Ciclosporin.

We will conduct a one-sided test for non-inferiority.³⁹ With 80% power and a significance level of 2.5%, 680 patients are required to test for this degree of non-inferiority using a one-sided chi-squared test without continuity correction. To account for a 10% drop-out or 5% cross-over, 750 patients (375 per arm) would need to be randomised in total. This sample size also gives over 90% power for claiming non-inferiority of PFS using a one-sided modified log-rank test with significance level 2.5% (at least 273 PFS events are required to assess non-inferiority with 80% power), and allows detection of a clinically relevant relative reduction of 50% (from 20% with Ir to 10% with IrCs) in the proportion of patients experiencing grade 3+ diarrhoea within 12 weeks of randomisation, with over 90% power and at a 5% (two-sided) significance level, using a two-sided chi-squared test without continuity correction.

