Kaplan Meier curves for overall survival and progression-free survival will be calculated, and differences between the treatment groups compared using one-sided modified log-rank tests. Survival will also be compared using multivariate modelling, Cox's Proportional Hazards model if appropriate, to adjust for the minimisation factors, previous anti-EGFR targeted therapy use and other important prognostic factors. HRs and corresponding 95% CIs will be presented. Sensitivity analysis will be considered to account for missing data for PFS analysis.

Patients' best response rate⁴² will be assessed by calculating the 95% CI of the difference in response rates between the two treatment groups. In addition, a one-sided chi-squared test for trend (or appropriate version) and logistic regression, to adjust for the minimisation factors,

previous anti-EGFR targeted therapy use and other prognostic factors, will be performed. Sensitivity analyses will be conducted to allow for any deaths from causes other than colorectal cancer, for whom no response status was observed.

Quality of life will be summarised using adjusted for baseline mean scores and 95% CIs for each EORTC QLQ-C30 domain, obtained from a multi-level repeated measures model, assuming missing data at random. Missing data patterns will be examined carefully, and if missing data patterns suggest data are missing not at random, analyses will also be carried out using pattern-mixture models, and data summarised using the Standardised Area Under the Curve. The MRC treatment value/acceptability supplement will be summarised descriptively with bar charts and summary tables for each question. The mean adjusted for baseline total Dermatology Life Quality Index score and scores for each domain will be presented with corresponding 95% confidence intervals.

To assess toxicity, the maximum grade per patient, rate per cycle and all cause mortality within 60 days of randomisation will be summarised descriptively for each treatment group. The difference between the two treatment groups in proportion of patients experiencing grade 3+ diarrhoea within 12 weeks of randomisation will be tested using a two-sided chi-squared test without continuity correction (or appropriate version), and 95% CI's will be presented. Logistic regression will also be used to adjust for the minimisation factors, previous anti-EGFR targeted therapy use and any other prognostic factors. Reasons for stopped treatment will be summarised.

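### The formal PFS non-inferiority claim for IrCs rests on 12-weekly scans that fall short of the protocol's own condition, and its log-rank test is mildly anti-conservative

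*Protocol*

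**What the plan says.** All references are to the Protocol.

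- **Section 10.4** explains why PFS is not the primary endpoint for Ir versus IrCs: "To use PFS for this purpose would require CT scanning at a frequency close to the difference being excluded". It puts that difference below 6 weeks. It chooses the 12-week progression-free proportion instead, which needs one mandatory scan.
- **Section 5.3** sets a scan at 12 weeks after randomisation, "then at 12-weekly intervals, or sooner if clinically indicated, until disease progression". Up to two further weeks are allowed for the 12-week scan. Section 6.3 keeps the later scans at 24, 36 and 48 weeks, even through a treatment break.
- **Section 11.1** gives the planning values: "median PFS was 4.2 months, with 63.3% of patients progression-free at 12 weeks", and "IrCs will be defined as no worse than Ir if median PFS is at least 3 months with IrCs". It then states: "This sample size also gives over 90% power for claiming non-inferiority of PFS", with the test, one-sided 2.5% level and 273-event requirement fixed in the same sentence.
- **Section 12** gives the analysis for OS and PFS: "differences between the treatment groups compared using one-sided modified log-rank tests". A Cox model with hazard ratios and 95% intervals is also planned. The only PFS sensitivity analysis mentioned concerns missing data.
- **Section 12.1** times the longer-term analysis at 273 PFS events together with a median follow-up of one year.
- **Section 10.2** lists PFS as secondary. **Section 2** names OS as the secondary measure that is to confirm non-inferiority.

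**The concern.** Section 10.4 sets a condition for using PFS to show non-inferiority, and the scan schedule does not meet it. PFS is still given a formal non-inferiority test with its own power statement, error rate and event trigger. A secondary endpoint can be less sensitive than the primary one, but a test with a stated 2.5% level should hold that level under the trial's own schedule.

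The direction of the error matters. Progression found at a scheduled scan happened at some point in the preceding interval. A log-rank test takes the scan date as the progression date, so many events share nearly the same time. Within such a cluster the comparison moves from a ratio of hazards towards a ratio of interval risks, and the latter is closer to 1. In a superiority test that costs a little power. In a test against a hazard ratio of 1.4 it makes a truly inferior regimen look closer to control, so a false non-inferiority claim becomes more likely than stated.

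**Working it through.** **Inputs.** From section 11.1: control median 4.2 months, limiting median 3.0 months, 12-week progression-free proportions 63.3% and 52.7%, 375 patients per arm, one-sided 2.5%. From section 5.3: 12-weekly scans and the two-week allowance. The share of events dated between scheduled scans, the spread of scan dates, the tie rule and exponential PFS are assumptions.

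**1. Schedule against condition.** The difference excluded is 4.2 − 3.0 = 1.2 months, or 1.2 × 52/12 = 5.2 weeks, which agrees with the protocol's figure of under 6 weeks. The scan interval is 12/5.2 = 2.3 times that.

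**2. Margin.** The ratio of medians is 4.2/3.0 = 1.40. The proportions agree: ln 0.527 / ln 0.633 = 1.401.

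**3. The plan's own event count.** Schoenfeld's formula gives 4(1.960 + 0.842)²/(ln 1.4)² = 277.3, so 278 events against the stated 273. With 273 events, power is 79.4%. Power of 90% needs 372 events, so the statement of over 90% with 750 patients is consistent. The planning figures are sound if event times are exact.

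**4. Direction.** At the margin, the 12-week event risks are 1 − 0.527 = 0.473 and 1 − 0.633 = 0.367. Their ratio is 0.473/0.367 = 1.29, below the hazard ratio of 1.40.

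**5. Size.** PFS was simulated at a true hazard ratio of 1.40 with 375 per arm and one year of follow-up (about 660 events). The test was the score test at 1.4, with score Σ[d_T − d·1.4·Y_T/(1.4·Y_T + Y_C)] and the plain (Breslow-type) variance, over 4,000 to 6,000 runs for most settings. At 6,000 runs the simulation standard error is √(0.025 × 0.975/6000) = 0.2 points near 2.5% and √(0.12 × 0.88/6000) = 0.4 points near 12%.

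| How progression is dated | False non-inferiority (nominal 2.5%) |
|---|---|
| All dates exact | 2.3–2.5% |
| All at scans, scan dates spread evenly over 2 weeks | 3.6% |
| Same spread, a quarter of events dated exactly | 3.4% |
| Half dated exactly, rest on a common scan day | 5.0% |
| A quarter dated exactly, rest on a common scan day | 7.6% |
| All on a common scan day | 12.1% |

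**6. What else moves it.**
- *Ties.* With every event on a common scan day, Efron's handling gives about 3%; the tie-corrected variance gives about 28%.
- *Number of events.* With every event on a common scan day and the plain variance, the rate is 5.0% at exactly 273 events and 8.7% at 500. Two years of follow-up gives 13.8%.
- *Censoring.* One two-week-spread run at one year gave 7.1%. There, progression-free patients were censored at the nominal 48-week date, ahead of events dated up to two weeks later. Censoring them at their own last scan brought a check run to 3.8%.

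**7. The alternative.** A complementary log-log grouped-time model on the 12-week grid, with the upper 95% limit compared with 1.4, gave false non-inferiority of 2.2–2.7% and power of about 98% at a true hazard ratio of 1, with 675 to 750 patients.

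**The case against.** The strongest reply is that the larger error rates are mostly an effect of ties. A multi-centre trial does not scan everyone on the same study day. Section 5.3 allows up to two weeks beyond week 12, allows earlier scans when clinically indicated, and asks for a CT when clinical progression appears between scheduled visits. PFS also counts deaths, which can be dated exactly. Once scan dates differ by a few days the rate falls to 3–5%. This stands. A reader might take 12% as the trial's error rate, or as a ceiling on it. The documents support neither reading: it is one extreme setting, and the result also depends on tie handling, which a statistical analysis plan not shown here may well fix.

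Second, section 10.4 is about the choice of primary endpoint, and the authors met the scan limitation by making PFS secondary. A reader might infer that the protocol declares PFS incapable of supporting the claim. It does not; it says what such use would require. What remains is that sections 11.1, 12 and 12.1 go on to plan that use as a formal test without meeting the requirement or adapting the method to it.

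Third, a reader might treat PFS as the main support for IrCs non-inferiority. Section 2 gives the confirming role to OS, and makes the tolerability questions depend on the primary endpoint. That also stands and limits the consequence.

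**Conclusion.** The point holds as a limited one about a secondary claim. The protocol says PFS non-inferiority would need scans at intervals close to a difference of under 6 weeks. It scans every 12 weeks, and still fixes a powered one-sided 2.5% modified log-rank claim on PFS.

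The plain-variance test exceeded 2.5% in every simulated setting with scan-dated events, always in favour of non-inferiority. With scan dates spread over the permitted two weeks the excess is about one percentage point (3–4% against 2.5%). It is larger only to the extent that events share scan days: about 5–8% with a quarter to a half dated exactly, and about 12% with none. These figures assume exponential PFS, about one year of follow-up and the stated dating patterns, none of which the protocol fixes.

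The primary comparison of 12-week progression-free proportions, its alpha and the 750-patient sample size are not affected.

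**What to change.** Choose one of two changes in sections 11.1 and 12.

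1. **Keep the claim and match the method to the schedule.** Base PFS non-inferiority on a grouped-time (complementary log-log) or interval-censored proportional hazards model. Declare non-inferiority if the upper limit of the two-sided 95% interval for the hazard ratio lies below 1.4, and state that margin explicitly. Keep the modified log-rank test as supportive.
2. **Drop the formal claim.** Report the PFS hazard ratio with its 95% interval descriptively, and remove the PFS non-inferiority power statement.

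Either way, a sentence in section 10.4 should say why PFS is still analysed although its scan-frequency condition is not met.

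The cost is analysis wording: no new scans, data or patients. In simulation the grouped model keeps power near 98% at a true hazard ratio of 1. A pure 12-week grid gives up the exact dating of deaths and of progressions found between scans; an interval-censored model that keeps exact dates where they exist avoids most of that loss.
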